5.1.2 Trial treatment Administration and Schedule

The trial Schedule of Assessments are presented in [Table 1](#) to [Table 7](#).

5.1.2.1 Induction Chemotherapy

Subjects enrolled in this trial will start with a 12-week chemotherapy Induction Phase comprised of oxaliplatin and either 5-FU or capecitabine (according to the dosing schedule in [Section 6.2.2](#) and [Table 1](#) and [Table 2](#) or in accordance to the label instructions and per local guidelines).

- Oxaliplatin at 85 mg/m² IV on Day 1 with leucovorin 200 mg/m² IV on Day 1 (or equivalent levoleucovorin dose) followed by 5-FU at 2600 mg/m² IV continuous infusion over 24 hours on Day 1, given every 2 weeks (for up to 12 weeks, [Table 2](#)).

OR

Oxaliplatin at 85 mg/m² IV on Day 1 with leucovorin 400 mg/m² IV on Day 1 (or equivalent levoleucovorin dose) followed by 5-FU at 400 mg/m² IV push on Day 1 and 2400 mg/m² IV continuous infusion over 46-48 hours (Days 1 and 2) given every 2 weeks (for up to 12 weeks)

OR

- Oxaliplatin at 130 mg/m² IV on Day 1 with capecitabine at 1000 mg/m², twice daily for 2 weeks followed by a 1-week rest period given every 3 weeks (for up to 12 weeks, [Table 1](#)).

Local label and guidelines should be followed for specific starting doses due to renal or hepatic impairments and for subsequent dose modifications due to different toxicities.

Subjects who experience a CR, PR, or SD after 12 weeks will be randomly assigned to either avelumab or continue the same regimen of chemotherapy from the Induction Phase. Subjects who demonstrate a response during the Induction Phase that renders their measurable disease no longer measurable at the time of the Maintenance Phase can be randomized.

5.1.2.2 Maintenance Therapy

5.1.2.2.1 Avelumab Arm

Subjects randomly assigned to the avelumab arm will receive IV infusion of avelumab (10 mg/kg over 1 hour) once every 2 weeks (see [Table 6](#)).

To mitigate infusion-related reactions, premedicate patients with an antihistamine and with paracetamol (acetaminophen) prior to the first 4 infusions of avelumab. Premedication should be administered for subsequent avelumab doses based upon clinical judgment and presence/severity of prior infusion reactions. This regimen may be modified based on local treatment standards and guidelines as appropriate provided it does not include systemic corticosteroids.

The formulation and packaging information of avelumab is provided in [Section 6.1.2](#), [Section 6.1.1](#) and [Section 6.6](#), respectively.

5.1.2.2.2 Chemotherapy Arm

Subjects randomly assigned to the maintenance chemotherapy arm will receive first-line chemotherapy according to the dosing schedule (see Section 6.2 and Table 3 to Table 4) or in accordance to the label instructions and per local guidelines) until disease progression, unacceptable toxicity, for the accepted maximal duration of the agent(s) selected, or any of the criteria for withdrawal from trial treatment is fulfilled (Section 5.5).

The dose and schedule during the Maintenance Phase are as follows:

Subjects randomly assigned to chemotherapy will continue the same regimen of oxaliplatin-fluoropyrimidine doublet as they received during the Induction Phase until disease progression.

- Subjects who are not deemed eligible to receive further chemotherapy will receive BSC alone with no active therapy. Prior to randomization, Investigators must specify BSC treatment for these subjects (see Table 5)
- For subjects receiving chemotherapy (oxaliplatin + 5-FU or oxaliplatin + capecitabine), dose modifications after the starting dose are allowed if the continuation of the oxaliplatin-fluoropyrimidine doublet, or a component thereof, is prohibited by toxicity. For subjects intolerant to further oxaliplatin, single-agent capecitabine or 5-FU + leucovorin will be an option for dose modification.

Additionally, in order to reduce the incidence and severity of nausea and vomiting as well as the severity of hypersensitivity reactions, subjects will be administered pretreatment prior to each therapy infusion per local institutional practice.

5.1.3 Dose Modification and Adverse Drug Reactions Requiring Treatment Discontinuation

5.1.3.1 Dose Modification for Avelumab

The dose of avelumab will be calculated based on the weight of the subject determined within 72 hours prior to the day of drug administration. The dose of avelumab used for the previous administration can be repeated if the change in the subject's weight is 10% or less than the weight used for the last dose calculation.

Each subject will stay on the avelumab-assigned dose of 10 mg/kg unless treatment needs to be stopped. Dosing modifications (changes in infusion rate) and dose delays are described in Section 5.1.3.2 and Section 6.5.4.1. There will be no dose reductions.

5.1.3.2 Adverse Drug Reactions Requiring Avelumab Discontinuation or Modifications

The following adverse drug reactions (ADRs, see Section 7.4.1.1) require permanent treatment discontinuation of avelumab:

- Any Grade 4 ADRs require treatment discontinuation with avelumab except for single laboratory values out of normal range that are unlikely related to trial treatment as assessed by the Investigator, do not have any clinical correlate, and resolve within 7 days with adequate medical management.
- Any Grade 3 ADRs require treatment discontinuation with avelumab except for any of the following:
 - Transient (≤ 6 hours) Grade 3 flu-like symptoms or fever, which are controlled with medical management
 - Transient (≤ 24 hours) Grade 3 fatigue, local reactions, headache, nausea, or emesis that resolve to Grade ≤ 1
 - Single laboratory values out of normal range (excluding Grade ≥ 3 liver function test increase) that are unlikely related to trial treatment according to the Investigator, do not have any clinical correlate
 - Grade 3 skin toxicity
 - Tumor flare phenomenon defined as local pain, irritation, or rash localized at sites of known or suspected tumor
 - Change in ECOG PS to ≥ 3 that resolves to ≤ 2 within 14 days (infusions should not be given on the following cycle, if the ECOG PS is ≥ 3 on the day of trial treatment administration).
 - Asymptomatic Grade ≥ 3 lipase or amylase elevation not associated with clinical manifestations of pancreatitis. Medical Monitor must be consulted for such lipase and amylase abnormalities.
- Any Grade 2 ADR should be managed as follows:
 - If a Grade 2 ADR resolves to Grade ≤ 1 by the last day of the current cycle, treatment may continue.
 - If a Grade 2 ADR does not resolve to Grade ≤ 1 by the last day of the current cycle, infusions should not be given on the following cycle. If at the end of the following cycle the event has not resolved to Grade 1, the subject should permanently discontinue treatment with an avelumab ADR (except for hormone insufficiencies, that can be managed by replacement therapy, for these hormone insufficiencies, up to 2 subsequent doses may be omitted).
 - Upon the second occurrence of the same Grade 2 ADR (except for hormone insufficiencies that can be managed by replacement therapy) in the same subject, treatment with avelumab has to be permanently discontinued.

Infusion-related reactions, hypersensitivity reactions, and flu-like symptoms (Grades 1 to 4), tumor lysis syndrome, and irAEs should be handled according to guidelines in Section 6.5.4.1, Section 6.5.4.2, Section 6.5.4.3, and Section 6.5.4.4.

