5.5 Criteria for Subject Withdrawal

5.5.1 Withdrawal from Trial Therapy

Subjects will be withdrawn from trial treatment during the Induction and/or Maintenance Phase for any of the following reasons:

- Subjects meeting the definition of PD while on-treatment based on RECIST v1.1. Subjects in the Maintenance Phase receiving avelumab who experience disease progression may continue treatment with avelumab if they meet the criteria presented in Section 6.2.1 (Investigator believes the subject will experience clinical benefit from the treatment and there is no unacceptable toxicity resulting from the treatment [See Section 6.2.1]. Such subjects will be withdrawn from the treatment if there is a subsequent scan/assessment of PD based on RECIST v1.1).
- Significant clinical deterioration (clinical progression), defined as new symptoms that are deemed by the Investigator to be clinically significant or significant worsening of existing symptoms
- Unacceptable toxicity
- Withdrawal of consent
- Occurrence of an exclusion criterion, which is clinically relevant and affects the subject's safety, if discontinuation is considered necessary by the Investigator and / or Sponsor
- Therapeutic failure requiring urgent additional drug (if applicable)
- Occurrence of any Grade ≥ 3 ADRs or repetitive Grade 2 ADRs as defined in Section 5.1.3.2 for subjects receiving avelumab.
- Occurrence of AEs, resulting in the discontinuation of the trial drug being desired or considered necessary by the Investigator and / or the subject
- Occurrence of pregnancy
- Use of a nonpermitted concomitant drug, as defined in Section 6.5.2, where the predefined consequence is withdrawal from the trial drug
- Noncompliance (see Section 6.9).

For subjects receiving avelumab, if discontinuation occurs due to progression and a definitive diagnosis/radiographic confirmation is not made at the time of discontinuation, a second imaging scan may be allowed for confirmation of progression. If progression at the second imaging scan is not confirmed and the subject wishes to restart, the subject will be allowed to continue receiving avelumab as long as they meet the criteria for continuation of treatment beyond progression. For more information, see Section 6.2.1.

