Investigators must also systematically assess the causal relationship of AEs to trial treatment using the following definitions. Decisive factors for the assessment of causal relationship of an AE to the trial treatment include, but may not be limited to, temporal relationship between the AE and the trial treatment, known side effects of trial treatment, medical history, concomitant medication, course of the underlying disease, trial procedures.

Unrelated: Not reasonably related to the IMP. The AE could not medically (pharmacologically/clinically) be attributed to the trial treatment under study in this clinical trial protocol. A reasonable alternative explanation must be available.

Related: Reasonably related to the IMP. The AE could medically (pharmacologically/clinically) be attributed to the trial treatment under study in this clinical trial protocol.

Abnormal Laboratory Findings and Other Abnormal Investigational Findings

Abnormal laboratory findings and other abnormal investigational findings (for example, on an ECG trace) should not be reported as AEs unless they are associated with clinical signs and symptoms, lead to treatment discontinuation or are considered otherwise medically important by the Investigator. If a laboratory abnormality fulfills these criteria, the identified medical condition (for example, anemia, increased ALT) must be reported as the AE rather than the abnormal value itself.

Adverse Drug Reaction

Adverse Drug Reactions are defined in this study as any AE suspected to be related to study treatment by the Investigator and/or Sponsor.

Serious Adverse Events

An SAE is any untoward medical occurrence that at any dose:

- Results in death.
- Is life-threatening. (Note: The term "life-threatening" refers to an event in which the subject is at risk of death at the time of the event, not an event that hypothetically might have caused death if it was more severe).
- Requires inpatient hospitalization or prolongs an existing hospitalization.
- Results in persistent or significant disability or incapacity.
- Is a congenital anomaly or birth defect.
- Is otherwise considered to be medically important.

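### Protocol 5.1.3.2 both requires and waives permanent discontinuation of avelumab for some asymptomatic Grade 4 lipase or amylase elevations, and its laboratory exceptions do not fit the definitions in 7.4.1.1

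*Protocol*

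**What the plan says.** Protocol 5.1.3.2 sets the rules for stopping avelumab permanently, by grade of ADR.

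- **Grade 4.** "Any Grade 4 ADRs require treatment discontinuation with avelumab except for single laboratory values out of normal range". That exception carries three conditions, the last to be met under suitable medical care: "unlikely related to trial treatment as assessed by the Investigator, do not have any clinical correlate, and resolve within 7 days". There is no other exception at Grade 4.
- **Grade 3.** "Any Grade 3 ADRs require treatment discontinuation with avelumab except for any of the following". The list that follows includes a laboratory exception ("excluding Grade ≥ 3 liver function test increase) that are unlikely related to trial treatment according to the Investigator", with no clinical correlate) and, as a separate item, "Asymptomatic Grade ≥ 3 lipase or amylase elevation not associated with clinical manifestations of pancreatitis". The lipase/amylase item sets no condition on relatedness or on time to resolution. Its next sentence makes consultation of the Medical Monitor mandatory.

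Protocol 7.4.1.1 gives the definitions on which these rules depend. "Adverse Drug Reactions are defined in this study as any AE suspected to be related to study treatment", and the sentence goes on to say that suspicion by the Investigator, the Sponsor or both is enough. The causality scale has two levels, Related and Unrelated. An abnormal laboratory finding is reported as an AE only if it comes with clinical signs and symptoms, leads to discontinuation, or is otherwise medically important in the Investigator's view.

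Protocol 5.5.1 makes the rule a withdrawal criterion by pointing back to it: "Occurrence of any Grade ≥ 3 ADRs or repetitive Grade 2 ADRs as defined in Section 5.1.3.2 for subjects receiving avelumab". Section 5.1.3.2 ends by referring immune-related events (irAEs) to 6.5.4.4. Table 11 there has no lipase or amylase row, but its generic Grade 4 row for other irAEs calls for permanent discontinuation.

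**The concern.** The lipase/amylase item sits under the Grade 3 bullet but is worded to include Grade 4, and the Grade 4 bullet does not mention it. A site can therefore find two opposite instructions in one section for the same laboratory result.

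The laboratory exceptions raise a second difficulty. They are exceptions to a rule about ADRs, which are suspected to be related, yet they apply only where the Investigator thinks the value unlikely to be related.

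At stake is a permanent stopping rule for the experimental drug. Sites that resolve the text differently would differ in how they manage subjects. They would also differ in avelumab exposure (SAP 14), in TEAEs leading to discontinuation (SAP 16.1.2), and in whether deviation code PROCED07, for treatment continued after withdrawal criteria were met, is recorded (SAP Appendix I).

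**Working it through.** No power, alpha or event figure is involved. The check applies the three texts (the Grade 4 bullet, the Grade 3 exception list and the ADR definition) to each type of event.

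**Step 1: which values are reached.** A value must first be an AE under 7.4.1.1. An asymptomatic value qualifies only if it leads to discontinuation or is judged medically important. It must then be suspected as related by the Investigator, the Sponsor or both to be an ADR.

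**Step 2: asymptomatic lipase or amylase ADRs.**

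| Case | Grade 4 bullet | Lipase/amylase item | Result |
|---|---|---|---|
| Grade 4, suspected by the Investigator | Stop: the unlikely-related condition fails | Waived | Conflict |
| Grade 4, suspected by the Sponsor only, not resolved within 7 days | Stop: the 7-day condition fails | Waived | Conflict |
| Grade 4, suspected by the Sponsor only, no clinical correlate, resolved within 7 days | Laboratory exception met | Waived | No conflict |
| Grade 3 | Does not apply | Waived | No conflict |

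The conflict therefore covers asymptomatic Grade 4 lipase or amylase ADRs that miss at least one of the three conditions of the Grade 4 laboratory exception.

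**Step 3: whether another section decides.** Section 5.5.1 only refers back to 5.1.3.2. Table 11 applies only if the event is judged an irAE; its generic Grade 4 row then adds a second text against the waiver.

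**Step 4: the laboratory exceptions for other tests.** If the Investigator suspects a relation, the value is an ADR but fails the unlikely-related condition, so the exception cannot apply at Grade 3 or Grade 4. If only the Sponsor suspects a relation, the value is still an ADR and the exception can apply, provided that its other conditions are met. Unlikely related is not a level of the Related/Unrelated scale, so the text does not say how a site should record such a judgement.

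**Step 5: how often the rule is consulted.** Table 12 places amylase and lipase in core chemistry. Table 6 schedules core chemistry at Weeks 1, 3, 5, 7, 9, 11 and 13 (7 panels), then every 2 weeks. Results are reviewed before dosing, so the Week 1 panel precedes the first avelumab dose: 7 − 1 = 6 panels by Week 13 can reflect avelumab.

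**The case against.** The best defence is that the item belongs to the Grade 3 list and so means Grade 3 only. The same list uses Grade ≥ 3 loosely for liver function tests. This reading is plausible, but it leaves the ≥ sign without effect, the text does not state it, and the flu-like symptom, fatigue and skin toxicity items in the same list say plain Grade 3.

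A second defence is the mandatory Medical Monitor consultation, which makes divergent handling between sites less likely. That stands as a safeguard. It does not say whether treatment stops, so the Medical Monitor faces the same two instructions.

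A third is that an asymptomatic laboratory value is not an AE by default. This also stands: it narrows the set of affected events but does not empty it.

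A reader might go further and infer that the laboratory exceptions can never apply to an ADR. The documents do not support that. An ADR can rest on the Sponsor's suspicion alone, while the exceptions turn on the Investigator's view, so an ADR suspected only by the Sponsor can qualify.

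**Conclusion.** Section 5.1.3.2 contradicts itself for a narrow but identifiable set: asymptomatic Grade 4 lipase or amylase elevations that are reported as AEs, are suspected to be related, and fall outside the Grade 4 laboratory exception. No other passage resolves the conflict. The laboratory exceptions at both grades also rest on a judgement that the causality scale does not contain, and they cannot reach an ADR that the Investigator suspects.

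The conclusion assumes that Grade ≥ 3 is read as written. On a Grade 3-only reading the contradiction goes away, and the mismatch in the laboratory exceptions remains.

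The number of subjects affected cannot be given, because the documents state no frequency of Grade 4 elevations. The 6 panels show how often a site must apply the rule, not how often it fails. A reader might infer an effect on the overall survival comparison or the per-protocol set, but neither is shown: PROCED07 is not marked clinically important in SAP Appendix I and is not among the per-protocol exclusions in SAP 9.

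**What to change.** Reconcile the Grade 4 bullet, the Grade ≥ 3 lipase/amylase item and the generic Grade 4 irAE row of Table 11, so that one instruction covers Grade 4. Reconcile the unlikely-related wording of the two laboratory exceptions with the ADR definition and the two-level causality scale in 7.4.1.1. Section 5.5.1 refers to 5.1.3.2 and would follow it. Which instruction stands is for the sponsor's medical team.

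The cost is a protocol clarification or a letter to sites still treating with avelumab, with no new assessments. It may still be of use although randomization is complete, since Protocol 7.1.4 provides for subjects on treatment beyond Week 109.

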5.1.3.3 Dose Modification for Chemotherapy

During the Induction Phase, dose modifications (dose delays and dose changes) for toxicity after the starting dose are allowed and should be made in accordance with labeling instructions and local institutional guidelines. Subjects on chemotherapy in the Maintenance Phase will continue with the same dose they had at the end of the Induction Phase (starting dose or reduced dose). During the Maintenance Phase, dose modifications are also allowed for toxicity.

The dose of chemotherapy will be calculated based on the weight or body surface area, as applicable, of the subject determined within 72 hours prior to the day of drug administration (see Table 9).

Dose modification guidelines (dose delays and dose changes) after the starting dose for chemotherapy are provided in Table 8. For specific starting doses due to renal or hepatic impairment and for subsequent dose modifications due to different toxicities, please follow the local label and guidelines.

For subjects intolerant to further oxaliplatin, single-agent capecitabine or 5-FU + leucovorin will be an option for dose modification.

Table 8 Dose Modification General Guidelines for Chemotherapy

Maintenance Therapy	First Dose Reduction	Second Dose Reduction	Third Dose Reduction
5-FU (2600 mg/m ² dose over 24 hours)	1950 mg/m ² - 2080 mg/m ² over 24 hours	1300 mg/m ² (1560 mg/m ² over 24 hours)	Discontinue
5-FU (2400 mg/m ² dose) over 46-48 hours	1800 mg/m ² - 1920 mg/m ² over 46-48 hours	1200 mg/m ² -1440 mg/m ² over 46-48 hours	Discontinue
Capecitabine	75% of starting dose	50% of starting dose	Discontinue
Oxaliplatin (85 mg/m ² dose)	64 to 68 mg/m ² in accordance with local label/institutional guidelines	42.5 mg/m ² in accordance with local label/institutional guidelines	Discontinue
Oxaliplatin (130 mg/m ² dose)	98 to 104 mg/m ² in accordance with local label/institutional guidelines	65 mg/m ² in accordance with local label/institutional guidelines	Discontinue

5-FU=5-fluorouracil

5.2 Discussion of Trial Design

5.2.1 Rationale Supporting the Choice of the First-line Chemotherapy

There is no consensus on what should be the optimal first-line chemotherapy for the management of advanced gastric cancer. A platinum fluoropyrimidine doublet is considered as an acceptable option by the National Comprehensive Cancer Network (NCCN), ESMO, and Japanese guidelines for the management of that disease (Waddell 2013). In the proposed study, all subjects will receive a platinum fluoropyrimidine doublet consisting of capecitabine or 5-FU and oxaliplatin. Subjects whose disease is at least stable will be randomly assigned to receive either avelumab (active arm) or will, per the judgment of the Investigator, receive subsequent cycles of the initial chemotherapy regimen until unacceptable toxicities or disease progression.

The administration of oxaliplatin and capecitabine or 5-FU as a first-line regimen for the treatment of advanced gastric cancer is acceptable for the following reasons:

- Study REAL-2 (Cunningham 2008) demonstrated that capecitabine and oxaliplatin are as effective as fluorouracil and cisplatin, respectively in patients with previously untreated gastric cancer. In terms of safety, oxaliplatin administration resulted in lower incidence of Grade 3 and 4 neutropenia, renal toxicity and thromboembolism but to slightly higher incidence of Grade 3 and 4 diarrhea and neuropathy. The safety profiles of 5-FU and capecitabine were similar.
- Capecitabine or 5-FU in combination with a platinum-based antineoplastic agent (cisplatin) was the chemotherapy backbone used in the TOGA study that supported the approval of trastuzumab for patients with gastric cancer with human epidermal growth factor receptor 2 positive (HER2+) disease.

- Oxaliplatin triggers a particular type of apoptotic deaths that is considered to be immunogenic and was preferred to cisplatin for the platinum component of the required chemotherapy doublet (Tesniere 2010).
- To have only oxaliplatin as the platinum salt will limit the risk of having a confounding factor on the primary endpoints as REAL-2 did not completely rule-out that cisplatin and oxaliplatin had exactly the same clinical efficacy.

